We will select anonymised patients from the CALIBER cohort [15], which links four sources of electronic health data in England: the Clinical Practice Research Datalink (CPRD) with primary healthcare records, the Hospital Episode Statistics (HES) with hospital discharge information, and the Office for National Statistics (ONS) mortality and social deprivation data.

A patient will be included if he or she: a) was registered between January 1, 1998, and September 2015; b) aged 30 years or older at study entry; c) had no record of

previous diagnosis of cardiovascular disease; d) had been followed up for at least one year before the study entry; e) had at least one uric acid measurement.

Exposure

The main exposure will be the baseline serum uric acid (SUA) level measured within one year of the study entry as recorded in primary care. If a patient had more than one measurement, the mean of the values will be taken. We will perform sensitivity analyses to use the SUA level recorded closest to the study entry.

Since gout is an important complication of hyperuricaemia and is associated with CVDs, we will also classify the patient state at baseline as with gout or with no gout, regardless of SUA levels, based on the diagnosis within one year of the study entry. Participants who developed new-onset gout during follow-up will be analysed according to their baseline status of no gout.

Covariates

The following baseline covariates will be considered:

- a) Sociodemographic: sex, age and index of multiple deprivation;
- b) Cardiovascular risk factors: body mass index, systolic blood pressure, high-density lipoprotein (HDL) cholesterol, low-density lipoprotein (LDL) cholesterol, triglyceride, and estimated glomerular filtration rate, smoking status, alcohol consumption;
- c) Medication use: any prescription in the year before index date of blood pressure lowering drugs (including diuretics, beta blockers, ACEIs, ARBs), statins, non-steroidal anti-inflammatory drugs (NSAIDs), aspirin, immunosuppressant drug, and in women only, oestrogen oral contraceptives and hormone replacement therapy;
- d) Comorbidities (defined by Read codes, a coded thesaurus of clinical terms used in the UK, in primary care data and by ICD-10 codes in hospital care data): Cancer, diabetes, asthma or atopy, COPD, connective tissue disease, inflammatory bowel diseases.

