For continuous variables (BMI, systolic blood pressure, and cholesterol), we will use the most recent value in the year before the study entry. For alcohol consumption, we will use the most recent record in the five years before entry to classify participants' drinking behaviour into five categories: non-drinkers (Read codes as "teetotaller" or "non-drinker"), former drinkers (Read codes as "stopped drinking alcohol" or "ex-drinker"), occasional drinkers (Read codes as "drinks rarely" or "drinks occasionally"), current moderate drinkers (Read codes as "alcohol intake within recommended sensible limits" or "light drinker"), and heavy drinkers (Read codes as "alcohol intake above recommended sensible drinking limits" or "hazardous alcohol use").

We will impute missing covariate values using multiple imputation, as implemented in the “mice” algorithm in the statistical package R. We will extract the following values of the continuous variables to use as auxiliary variables for multiple imputation: the first measurement after the time window and the most recent measurement before the time window, along with the timing of these measurements relative to the study entry. We will check whether the imputations are plausible by comparing plots of the distribution of recorded and imputed values of all variables.

Follow up

The observation period for all participants will begin on the date when all the study inclusion criteria are fulfilled. Participants will be followed up until the occurrence of an initial presentation of cardiovascular disease, death, or de-registration from the practice, whichever occurred first.

Endpoints

Endpoints will be the initial presentation of cardiovascular disease as any of the following 13 CVDs diagnosed in primary care (defined by Read codes), secondary care (defined by ICD-10 codes), or at death.(defined by ICD-10 codes): Stable angina, unstable angina, myocardial infarction, unheralded coronary heart disease death, heart failure, cardiac arrest/sudden cardiac death, transient ischaemic attack, ischaemic stroke, subarachnoid haemorrhage, intracerebral haemorrhage, peripheral arterial disease, abdominal aortic aneurysm, atrial fibrillation, and a composite total cardiovascular disease (all 13 cardiovascular diseases combined). An example is given by the definition of atrial fibrillation [16]

Statistical analysis

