We will analyse the SUA level as a categorical variable in order to avoid presuming a particular shape for the association with CVDs. Since the normal range for SUA and the diagnosis cut-off for hyperuricemia diagnosis varies [17-19], we will use the following cut-offs:

- 1) 3 mg/dL (180 umol/L, the lower limit of target SUA level for long-term management recommended by the 2016 updated EULAR guideline [20]),
- 2) 4 mg/dL (240 umol/L),
- 3) 5 mg/dL (300 umol/L, the target SUA for severe cases or patients with tophi recommended by various guidelines [20-23]),
- 4) 6 mg/dL (360 umol/L, the general target SUA for long-term management recommended by various guidelines [20-23]),
- 5) 7 mg/dL (420 umol/L).

If the shape of the association between SUA and CVDs is found to be linear, we will then perform analyses with SUA level as a continuous variable.

Quantitative variables will be summarized in mean and standard deviation and qualitative variables in number and percentages. Between group differences of

parametric values will be compared using analysis of variance (ANOVA) and that of categorical variables using chi-square tests.

We will plot crude cumulative incidence curves for each specific cardiovascular endpoint for people with SUA levels between 240-300 umol vs. 360-420 umol/L, using age as the timescale, under a competing risks framework (i.e., participants could experience only one initial presentation).

We will use multivariable Cox regression to calculate cause-specific hazards for associations between categories of SUA levels and initial presentations of cardiovascular disease. We will plot Schoenfeld residuals to verify the proportional hazards assumption.

In the primary analysis, we will adjust for age (linear and quadratic), sex, index of multiple deprivation, diabetes, smoking status, BMI, systolic blood pressure, HDL cholesterol, LDL cholesterol, and prescription of statins or antihypertensive medication in the year before study entry. The baseline hazard function of each model will be stratified by general practice and sex, and we will use multiple imputation to account for missing covariate data.

Assuming independence in effects, heterogeneity in associations across CVD endpoints for the fourth vs. the first quintile will be assessed with tau-square statistic, which is the between-CVD endpoint variance, and I^2 that can be interpreted as the proportion of the total variation in estimates that is due to heterogeneity.

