We will conduct a series of sensitivity analyses:

- a) Covariate adjustment: We will conduct analyses adjusted for age and sex only, and analyses adjusted for age, sex, and cardiovascular risk factors. We will assess interactions with age and sex.
- b) Gout: We will categorise patients into with gout and with no gout, regardless of SUA.
- c) Imputed data: We will check whether the imputations are plausible by comparing plots of the distribution of recorded and imputed values of all variables.
- d) Data source: We will conduct analysis ignoring endpoints recorded only in primary care (CPRD).
- e) Endpoints: We will conduct analysis restricting endpoints to fatal endpoints.
- f) Time: We will conduct analysis restricting participants to individuals who entered the study after 2004 (when recording of covariates would be expected to be more complete after introduction of the Quality and Outcomes Framework to incentivise good performance in the care of specified diseases).

We will conduct all analyses using R 3.4.1.

Role of funding

The funders had no role in the study design, data collection, data analysis, data interpretation, or writing of the report.

References

[5] Kavousi, M. et al. Evaluation of newer risk markers for coronary heart disease risk classification a cohort study. *Ann Intern Med*. 156, 438–444 (2012).

[6] Storhaug, H. et al. Uric acid is a risk factor for ischemic stroke and all-cause mortality in the general population a gender specific analysis from The Tromso Study. *BMC Cardiovasc Disord*. 13, 115 (2013).

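### Entry is spread over about 17.7 years, but no Cox model contains a calendar term, so secular change may confound the SUA hazard ratios; year of entry should be added as a covariate

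*Protocol*

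**What the plan says.** Under Study population, a patient is eligible if he or she "was registered between January 1, 1998, and September 2015", "had been followed up for at least one year before the study entry" and "had at least one uric acid measurement". Under Follow up, "The observation period for all participants will begin on the date when all the study inclusion criteria are fulfilled". Entry is therefore individual and staggered, and only patients who have been tested enter.

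The candidate covariates under Covariates begin with "Sociodemographic: sex, age and index of multiple deprivation" and go on to risk factors, medication and comorbidities. None is a calendar variable. Under Statistical analysis the primary model is given in full: "we will adjust for age (linear and quadratic), sex, index of multiple deprivation, diabetes, smoking status, BMI, systolic blood pressure, HDL cholesterol, LDL cholesterol", plus statin or antihypertensive prescription in the preceding year. Then: "The baseline hazard function of each model will be stratified by general practice and sex". Sensitivity analysis (a) has two further adjustment sets, one of age and sex alone and one that adds cardiovascular risk factors.

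Calendar time appears once among the analyses, in sensitivity analysis (f), which keeps only "individuals who entered the study after 2004 (when recording of covariates would be expected to be more complete" because of the primary care incentive scheme).

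**The concern.** Stratifying by practice compares patients within the same practice, so stable differences between practices drop out. Two patients of one practice who entered a decade apart remain in the same stratum and are compared as if the background hazard and the reasons for testing were the same in both years. Age at entry is not a substitute, since people of the same age enter in every year.

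Two features of the design make this relevant. A uric acid test is a condition of entry, so a change over the years in who is tested could change the SUA mix of the cohort. Endpoints include diagnoses coded in primary care, so changes in coding could change recorded rates. If both happen, entry year is a common cause of SUA category and of the recorded event rate.

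The study sets out to estimate associations for 13 separate presentations and to measure heterogeneity across them with tau-square and I². Endpoints whose rates trend in opposite directions would be biased in opposite directions, and that difference would enter the heterogeneity estimate.

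**Working it through.** The protocol gives no figure to reproduce on this point. The check covers the dates, the model contents and an illustrative bias.

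**Dates (Study population; sensitivity analysis (f))**
- 1 January 1998 to 30 September 2015: 17.7 years.
- For someone newly registered in January 1998, the required prior year moves the earliest entry to January 1999, leaving 16.7 years.
- After restriction (f): 1 January 2005 to 30 September 2015 is 10.7 years (11.7 if 2004 counts as included).

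**Model contents**

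| Model | Adjustment | Calendar term |
|---|---|---|
| Primary | Age, age squared, sex, deprivation, diabetes, smoking, BMI, SBP, HDL, LDL, statins or antihypertensives | None |
| Sensitivity (a), first set | Age, sex | None |
| Sensitivity (a), second set | Age, sex, cardiovascular risk factors | None |
| Strata of the baseline hazard | Practice, sex | None |

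**Illustrative bias**

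All inputs here are assumptions. Take two entry periods 8.5 years apart and a true SUA hazard ratio of 1.0. Let pH and pR be the shares of the high and reference SUA bands that entered in the early period, g the annual log trend in the endpoint rate, and k = exp(8.5 × g). With no covariate adjustment,

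bias factor = (pH + (1 − pH)k) / (pR + (1 − pR)k)

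| pH, pR | g | k | Calculation | Factor |
|---|---|---|---|---|
| 0.60, 0.45 | −0.03 | 0.775 | 0.910 / 0.876 | 1.039 |
| 0.60, 0.45 | −0.05 | 0.654 | 0.862 / 0.810 | 1.064 |
| 0.60, 0.45 | +0.03 | 1.290 | 1.116 / 1.160 | 0.962 |
| 0.50, 0.45 | −0.01 | 0.919 | 0.959 / 0.955 | 1.004 |
| pH = pR | any | any | numerator = denominator | 1.000 |

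As a cross-check with a steady trend, the factor is (1 + g)^(−d), where d is the difference in mean entry year between bands. A 3% annual fall gives 0.97^(−1) = 1.031 for d = 1 and 0.97^(−3) = 1.096 for d = 3. The 60% versus 45% split corresponds to d = 0.15 × 8.5 = 1.3 years, so the 1.039 above is consistent with this; d = 3 is a much stronger imbalance.

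Across endpoints, two with true hazard ratio 1.0 and trends of −5% and +3% would differ by 1.064 / 0.962 = 1.11.

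**After restriction (f)**

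Split the remaining 10.7 years into halves 5.35 years apart and take g = −0.03, so k = 0.852. Then 60% versus 45% gives 0.941 / 0.918 = 1.024, and 50% versus 45% gives 0.926 / 0.918 = 1.008. The restriction shrinks the bias but does not remove it.

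**The case against.** A reader might infer that the SUA hazard ratios are confounded by calendar time, biased upward for endpoints with falling rates and downward for those with rising rates. The protocol does not support that. It says only that covariate recording is expected to be more complete after 2004. It does not say that uric acid testing was incentivised, that early testing was more selective, that early entrants had higher SUA, or that any endpoint rate rose or fell. Confounding needs both links to hold after adjustment, and the direction rests on an assumed association between early entry and high SUA. This objection stands, and the point is therefore conditional.

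The bias figures also describe an unadjusted comparison. Blood pressure, lipids, smoking, statins and antihypertensives are in the primary model and may carry much of any secular change. If, as an assumption, half of a 3% annual fall were absorbed, 1.039 would become 1.019. This stands too: the figures are not estimates of the residual bias.

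Third, planned analyses bear on the issue. Analysis (d), which ignores endpoints recorded only in primary care, and (e), which uses fatal endpoints only, bear on drift in primary care coding. Analysis (f) removes the one period break the document identifies, and comparing it with the full cohort would give a partial indication. But (d) and (e) do nothing about a changing SUA mix or real trends in incidence, (f) is restriction rather than adjustment, and none of them alters the primary estimate.

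Lastly, this could be called a preference for one more covariate that an unseen analysis plan might supply. The protocol contains no contradiction here. It does, however, fix its primary model down to the quadratic age term and the strata, so the omission lies in what it specifies.

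**Conclusion.** The point holds as a conditional weakness. Entry is staggered over a window of about 17.7 years, and no specified Cox model includes or stratifies by calendar time. Secular change may therefore confound the SUA hazard ratios, with a sign that can differ between endpoints. Whether it does cannot be determined from the document.

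On the assumed inputs the distortion is about 0.4% to 6% before covariate adjustment, and nil if SUA category is unrelated to entry period. The document offers no benchmark for judging whether a shift of that size would change a conclusion. The case for acting rests on the low cost of the remedy and on the study's interest in differences between endpoints, not on a demonstrated bias or an error in any stated figure.

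**What to change.** Add calendar year of study entry to the adjustment set of the primary Cox model and of both sensitivity (a) models, as a spline or in 3-year bands. A covariate is preferable to further strata, because practice-by-sex strata are already fine and splitting them by period could leave many with few events. Keep sensitivity analyses (d), (e) and (f) as they are.

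The cost is one additional term. Entry date is known for every participant, so nothing has to be imputed, and the loss of precision should be negligible. If entry year is not a confounder, the estimates should barely move.
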